3 OBJECTIVES AND ENDPOINTS

OBJECTIVES Impact of the intervention on:	ENDPOINTS	GUIDELINE JUSTIFICATION FOR ENDPOINTS*
Primary		
1. provider-diagnosed CKD for patients with no documented CKD diagnosis (recognition care gap)	1. Provider-diagnosed CKD in the 18-month period after an index visit	(a) Diagnostic classification of CKD based on eGFR and albuminuria category;
2. ACEI/ARB orders for patients with diagnosed hypertension or nephropathy and no current ACEI/ARB (ACEI/ARB care gap)	2. ACEI/ARB orders in the 18-month period after an index visit	(b) use of ACEIs or ARBs in adults with diabetes and UMACR 30-300 mg/g OR all patients with UMACR >300 mg/g;
3. recommended BP control for patients with consecutive elevated BP (BP care gap)	3. Recommended BP control by the end of the 18-month period after an index visit	(c) BP control to <140/90 mm Hg in adults with CKD and normal UMACR <30 mg/g OR <130/80 mm Hg in adults with ACR >300 mg/g;

OBJECTIVES Impact of the intervention on:	ENDPOINTS	GUIDELINE JUSTIFICATION FOR ENDPOINTS*
4. recommended blood glucose control for patients with elevated A1c (glucose care gap)	4. Recommended blood glucose control by the end of the 18-month period after an index visit	(d) Glycemic control using individualized A1C targets of less than 7% or less than 8% in patients with limited life expectancy, cognitive impairment, or increased risk of hypoglycemia;
5. rates of consultation with nephrology for patients with stage 4 CKD or stage 3b CKD and UMACR >30 mg/g and no recent consultation with a nephrologist (nephrology care gap)	5. Nephrology consultation in the 18-month period after an index visit	(e) Timely nephrology care
Secondary		

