5 STUDY POPULATION

5.1 INCLUSION CRITERIA

Clinics are the primary unit of randomization. Medical group leaders at HPMG and PN agreed to enroll at least 30 primary care clinics in this study and provided letters of support. In order to be eligible for the study, a clinic was required to meet the following requirements:

- 1) Be a HealthPartners Medical Group or Park Nicollet care system clinic
- 2) Have an established adult primary care department within the clinic (family medicine, adult medicine, and/or combined pediatrics/internal medicine)
- 3) Have a minimum of 20 study eligible patients
- 4) Have access to a nephrologist or nephrology clinic within reasonable geographic proximity

Eligible Adult Patients:

Patients with an encounter with a primary care provider (general internist, family medicine physician, advanced practice nurse or physician assistant) at a study clinic were eligible for the CKD-CDS if the following criteria were met:

- 1) Aged 18 to 75 years, inclusive on their index date. The evidence-based guidelines on which the CDS intervention is based are not applicable outside this age range.⁶²
- 2) Have laboratory evidence of CKD based on eGFR values <60 cc/min/1.73m², including the most recent eGFR value on or prior to index date, and the closest previous eGFR done at least one week prior
- 3) Have one or more CKD care components suboptimally managed at the time of the index visit.

		suboptimally managed if
CKD recognition care gap	1.1) CKD not documented in the electronic health record	1.1) ICD-10 codes N18.3, N18.4, N18.5, N18.6, N18.9 at <2 outpatient encounters, and not on the problem list, in the previous 2 years
ACEI / ARB care gap	2.1) stage 3 CKD; and 2.2a) diagnosed hypertension, or 2.2b) nephropathy; and 2.3) no evidence of hyperkalemia; and 2.4) ACEI / ARB not current at index	2.1) eGFR 30-<60 cc/min/1.72m ² ; and 2.2a) ICD-10 codes I10, I11.x, I12.x, I13.xx, I15.x, I16.x at 1 inpatient or 2 outpatient encounters, or on the problem list, in the previous 2 years, or 2.2b) UMACR >= 30 mg albumin / g creatinine ; and 2.3) no ICD-10 code E87.5 or serum potassium >= 6.5 mg / dl in the previous 2 years; and 2.4) no ACEI / ARB orders with start date before or on index date, or end date on or after index date
BP care gap	3.1) 2 consecutive elevated BP	3.1) index BP and next most recent BP >= 130/80 mm Hg

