Glucose care gap	4.1) diagnosed diabetes; and 4.2) A1c above goal	4.1) ICD-10 codes E10, E11 at 1 inpatient or 2 outpatient encounters, or on the problem list, in the previous 2 years; and 4.2) most recent A1c>=7 on or before index date
Nephrology care gap	5.1) Stage 3b or 4 CKD; and	5.1a) most recent eGFR15-<30 cc/min/1.72m ² , or

	5.2) nephrology referral needed	5.1b) eGFR30-<45 cc/min/1.72m ² and UMACR >=30 mg/g; and 5.2) no completed nephrology visit in prior year
--	---------------------------------	---

The index visit is defined as the first visit at any randomized clinic during the accrual period at which the patient met these CKD-CDS intervention eligibility criteria and none of the exclusion criteria. The patient accrual period (for index visits) was 11 months, followed by a 18-month observation period, so that patients will have 18 to 29 months of post-index follow up (estimated median, 24 months).

Each patient was assigned to the clinic where their index visit took place and by extension to the randomized treatment group of that clinic. Patients with index visits at clinics randomized to the CKD-CDS intervention (or usual care) group were considered CKD-CDS intervention (or usual care) patients. A patient could have post-index visits, that may or may not be intervention eligible, at clinics randomized to the other treatment group. Following intent to treat principles, the patient's treatment group assignment will not change as a result of the clinic treatment group assignment or patient intervention eligibility at the post-index visits. Additionally, the index visit marks the beginning of each patient's 18-month observation period.

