Web-based eligibility algorithms assess eligibility at all visits in all randomized clinics for the duration of the intervention period. As a result, all patients who have visits during the intervention period will be universally and consistently screened for intervention eligibility without any action, or even awareness, from clinic staff. There is no consenting process for accruing patients into the study, except that patients who have requested to be excluded from all research will be excluded from the study analyses. In sum, neither the patients, clinicians nor study team can influence when a visit is identified as an index visit; and patients who exclude themselves from research are excluded from outcomes analyses. These factors combined minimize the risk of selection into the study denominator to the extent that virtually all intervention eligible patients are included.

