5.4 SCREEN FAILURES

All visits at all randomized clinics are screened for intervention eligibility via the CKD-CDS eligibility algorithms for the duration of the study. The IRB waived written informed consent for patients so those who meet inclusion and exclusion criteria based on then-current electronic medical record data are said to have an index visit and included in the study. The only exception to universal eligibility screening is the rare occasion when a network-wide outage or other large-scale event prevents the algorithms from running. Such events are exceedingly rare, and we assume that unscreened yet eligible patients are equally distributed across treatment groups.

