6 STUDY INTERVENTION

6.1 STUDY INTERVENTION(S) ADMINISTRATION

6.1.1 STUDY INTERVENTION DESCRIPTION

Intervention Clinics/Patients: The CKD-CDS intervention provides updated clinical recommendations at any primary care visit for study-eligible patients; at intervention clinics these are seen by PCPs and patients as described. At usual care clinics, the CDS output is not displayed or accessible to PCPs or patients but is archived electronically for analysis purposes. The CDS presents to patients and their PCP an evolving array of timely, evidence-based treatment options to improve CKD care (see Figure 2 below). Treatment options are patient specific, tailored to the patient's current clinical state, and evolve over time as the patient's clinical state evolves, or when evidence-based guidelines evolve. As described in detail above, the CKD-CDS intervention proposed in this project is rooted in a series of antecedent studies that developed more limited but successful forms of CDS.^{40, 63, 64} From an operational point of view, implementing CKD-CDS at intervention clinics requires a series of 4 distinct steps that occur at every encounter as described in Figure 2 below.

Step 1: Data exchange and evaluation: The EHR securely exchanges data with the Web Service at every encounter of patients aged 18-75 triggered by BP entry or chart opening for video and phone visits.

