Step 2: Recognition of CKD and presence of care deficits: Patients with stage 3-4 CKD are automatically identified by the Web Service and evaluated using algorithms maintained in the Web service for identification of CKD and for the 5 emphasized care gaps (identification of CKD, BP control, glucose control, ACEI/ARB use if appropriate, , and nephrology consultation if appropriate). If the patient has a care gap, the rooming staff receives an immediate BPA prompt to print CDS materials for the patient and the provider to review and use for shared decision making. Using a sequence of steps successfully implemented in previous studies, the rooming staff will print the materials and give the lay version to the patient to review while waiting for the provider. A professional version is left on the door for the provider to review before entering the exam room. This approach has been well-liked by our providers to help them be prepared and to engage patients in their care needs before the clinician-patient interaction. PCPs can also optionally view an electronic version of the CDS materials. The CDS can be viewed in real time for any patient by clicking on a button programmed in the EHR encounter display.

Step 3: Use of CKD-CDS recommendations as shared decision-making tools: The participating providers and all rooming staff in the intervention clinics will be trained in the use of the provider (professional) and patient (low-literacy) versions of the CKD-CDS. For this study, the CDS tool will be adapted to emphasize CKD and, for each identified deficit in CKD care, the CKD-CDS will display patient-specific recommendations consistent with then-current national CKD clinical guidelines; for example: (a) recognize CKD and ask the PCP to enter a CKD diagnosis on the problem list if indicated, and/or (b) specific considerations for how to modify BP control, glucose control, or ACEI/ARB therapy, and/or (c) refer certain patients to nephrology when referral criteria are met. The PCP assesses patient preference for any of the CKD-related treatment options. If the patient wants to act on 1 or more, the PCP can address it then or schedule a subsequent visit for that purpose. If the patient is not interested in any

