Usual Care Clinics: All control clinics/patients will continue to use the basic EMR-linked CDS for CV risk factor management. This CDS system includes algorithmically derived identification of high CV risk patients and prioritized treatment suggestions for lipids, BP, glycemic control, weight, tobacco, and aspirin use based on distance from goal, current medications, comorbid conditions, labs, allergies, and safety considerations.⁷¹⁻⁷⁶ The basic CDS does not include information specific to CKD care. Important to note is that the CKD-CDS tool will be running silently (in the background) at all clinics randomized to the Usual Care arm of the study. However, only the results of algorithms run by the basic EMR-linked CDS for CV risk factor management will be displayed in the Usual Care clinics. Running CKD-CDS silently in Usual Care clinics ensures that identification of study-eligible patients, and collection of primary outcome data will be done identically across all randomized clinics. Our ability to control the display of the CKD-CDS tool by clinic ensures that patients in Usual Care clinics continue to receive current standard of care (CDS for CV risk) and prevents intervention contamination at Usual Care clinic visits.

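### The rule that sets the H2 denominator (Section 5.1, item 2.4) joins two date tests with *or*, so as plainly read it excludes patients whose ACEI/ARB was stopped before index, contrary to its own label

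*Combined protocol and SAP*

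**What the plan says.** Objective 2 (Section 3) concerns "ACEI/ARB orders for patients with diagnosed hypertension or nephropathy and no current ACEI/ARB (ACEI/ARB care gap"). Section 9.3 places a patient in each of H1 to H5 according to the Section 5.1 care gaps present at index, so the ACEI/ARB gap is the entry rule for H2.

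In the Section 5.1 care-gap table, the descriptive column for item 2.4 says that the drug is not current at index. The operational column says "no ACEI / ARB orders with start date before or on index date, or end date on or after index date". No other section defines a current order at index or says what to do with an order that has no end date.

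The H2 outcome (Section 9.1) counts ACEI/ARB orders with a start or end date from the index date through 18 months. Item 2.4 and the outcome therefore both include the index date.

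On timing, the index visit is "the first visit at any randomized clinic during the accrual period at which the patient met these CKD-CDS intervention eligibility criteria", and Section 5.4 adds that "those who meet inclusion and exclusion criteria based on then-current electronic medical record data are said to have an index visit". Section 8.1 names the CKD-CDS tool as the source of care gaps at index and the health record as the source of ACEI/ARB orders.

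**The concern.** An order is current at index if it has started and has not yet ended. Item 2.4 requires that no order meet the first test or the second. A patient whose only order began and ended before index has nothing current, yet that order meets the start-date test and the patient is excluded.

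This matters because H2 is one of five primary hypotheses. Followed as written, the rule would estimate the effect in patients with no earlier order, while the objective and the row label promise an effect in patients without a current one. Two analysts working from the same table could build different H2 populations. For a patient whose only gap is this one, item 2.4 also decides whether an index visit exists at all.

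**Working it through.** **1. The logic.** Let *s* and *e* be an order's start and end dates and *t* the index date. Test A is *s* ≤ *t*; test B is *e* ≥ *t*. Current means A and B. The plain reading of item 2.4 is that no order meets A or B. A dated order escapes both tests only if *s* > *t* and *e* < *t*, which would put its end before its start. So the plain rule reduces to no ACEI/ARB order at all among the orders it can see. Example: an order from day −300 to day −100 meets A and fails B; the patient is not current but is excluded.

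**2. Readings side by side.** *Distributive* means: no order meeting A, or no order meeting B. *Reworded* means: no order with *s* < *t* and *e* ≥ *t*, computed from orders that predate the visit.

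| Order history | Plain | Distributive | Reworded |
|---|---|---|---|
| *Orders visible at screening* | | | |
| Never ordered | in | in | in |
| Stopped before index | **out** | in | in |
| Spans index, end date recorded | out | out | out |
| Started earlier, no end date | out | in, unless a blank means ongoing | set by the stated rule |
| First order written during or after the index visit | in | in | in |
| *Completed orders, all with end dates* | | | |
| Starts on the index date | out | out | in |
| Starts after index | **out** | in | in |
| Stopped, then restarted after index | **out** | out | in |

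The last three histories are H2 successes under Section 9.1. They are lost only if gap status is rebuilt from completed orders.

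**3. The plan's own H2 figure.** Inputs from Section 9.2 and Table 2: N = 9,012, 30 clinics, ICC .001 to .01, rates 50 to 60%, power .80, two-sided .05. Neff = N / [1 + (N/30 − 1) × ICC], half per arm, two-proportion formula with pooled variance under the null.

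- ICC .001: design effect 1.299, Neff 6,936, detectable difference 3.36 (rate 50%) and 3.27 (60%).
- ICC .01: design effect 3.994, Neff 2,256, detectable difference 5.88 (50%) and 5.70 (60%).

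This gives 3.3 to 5.9 points against the printed 3.4 to 5.7, close enough to use the same method below.

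**4. The group the label describes.** Table 1, row B, stage 3 patients without a current ACEI/ARB: 3,263 × (1 − .594) + 1,470 × (1 − .569) = 1,324.8 + 633.6 = 1,958 in 17 clinics. Prorated: 1,958 × 30/17 ≈ 3,456. This is an upper figure, taken before the age-75 and hyperkalemia limits.

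**5. What the plain reading would remove.** The share of stopped users is not in the documents; the shares below are assumptions.

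| Assumed share stopped | N left | Detectable difference (points) | Added by *or* |
|---|---|---|---|
| 0% | 3,456 | 4.9–7.0 | – |
| 10% | 3,110 | 5.1–7.1 | about 0.2 |
| 25% | 2,592 | 5.5–7.5 | 0.5–0.7 |
| 50% | 1,728 | 6.7–8.4 | 1.4–1.9 |

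Table 2 calls 10 points meaningful for this outcome. The share of stopped users would have to reach about 70 to 79% before the detectable difference reached 10. With 32 clinics instead of 30, the 0% row is 4.9 to 6.8 and the 50% row 6.7 to 8.3.

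**The case against.** The strongest reply is that the plain reading is the least coherent one. Apart from future-dated orders, every order visible at screening has already started, so the start test does all the work and the end-date clause is idle. The row label, Objective 2 and Table 1 all speak of current use. The distributive parse gives the labelled population on screening-time data when end dates are recorded. This looks like a drafting slip. That stands as an account of intent, and it is why the defect is placed in the written definition and not in what was run. It does not remove the defect: the plan does not select the looser parse, and that parse keeps a current user whose order has no end date unless a blank is taken as ongoing.

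Item 2.4 has no two-year look-back, unlike items 1.1, 2.2a, 2.3 and 4.1. That is no fault in itself: a test of currency needs none.

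A reader might infer that the rule biases the arm comparison by discarding patients started on treatment at the index visit. The documents point away from this. Data exchange occurs "at every encounter of patients aged 18-75 triggered by BP entry or chart opening for video and phone visits", and "If the patient has a care gap, the rooming staff receives an immediate BPA prompt to print CDS materials", so gap status is fixed before the clinician acts. Section 5.1 says that "neither the patients, clinicians nor study team can influence when a visit is identified as an index visit", and the tool runs silently in usual care so that "identification of study-eligible patients, and collection of primary outcome data will be done identically across all randomized clinics". On that source the loss of index-visit starters is zero. It arises only if the gap is rebuilt from completed orders, which no sentence prescribes and none forbids for item 2.4.

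**Conclusion.** The point holds as a defect in the written definition of a primary analysis population. Plainly read, item 2.4 contradicts its label and Objective 2, and H2 would apply to patients with no earlier ACEI/ARB order. It should be fixed. Confidence is medium, because a looser parse exists and the programmed flag is not shown.

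Three stronger conclusions are not supported. That the trial used the wrong population: the documents do not show which reading was implemented. That the comparison is biased: the rule is the same in both arms and, on the screening output, is applied before the tool can influence that visit. That H2 loses adequate power: at assumed shares of 10 to 50% the detectable difference is about 5.1 to 8.4 points, still below 10. These sizes rest on Table 1 prorated to 30 clinics, Table 2's rates and ICCs, and the assumed shares. The main effect is on whom H2 describes.

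**What to change.** For the H2 analysis population, reword item 2.4 as: no ACEI/ARB order with start date before the index date AND end date on or after the index date. Add a stated rule for orders without an end date. Say that gap status is taken from orders that predate the visit, that is, from the tool's screening output, so that orders written at the index visit count only as outcomes. This also reconciles the index-date overlap between Sections 5.1 and 9.1; the H2 outcome needs no other change.

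Then check the programmed flag against this definition.

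- If the flag tested currency, only the wording changes.
- If it followed the plain reading, keep the flagged patients as the primary H2 population and describe them as having no earlier ACEI/ARB order. Report how many accrued patients with only stopped orders were left out, and add them in one sensitivity analysis. Note there that the tool shows recommendations for identified deficits (Section 6.1.1), so these patients may never have been shown an ACEI/ARB recommendation and including them may dilute the effect. State also that patients whose only gap was this one have no index visit and cannot be recovered.

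The cost is wording in Sections 5.1, 9.1 and 9.3, a check of the flag and extraction code, and at most one added analysis. No new data are needed.

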5.2 EXCLUSION CRITERIA

An individual who meets any of the following criteria will be excluded from receiving the CKD-CDS:

- 1) Patients enrolled in hospice,
- 2) Patients with active cancer (3 or more diagnosis codes in last year) or undergoing parenteral chemotherapy
- 3) Patients with pregnancy in the last year
- 4) Patients with end stage renal disease

5.3 LIFESTYLE CONSIDERATIONS

Not applicable

5.4 SCREEN FAILURES

All visits at all randomized clinics are screened for intervention eligibility via the CKD-CDS eligibility algorithms for the duration of the study. The IRB waived written informed consent for patients so those who meet inclusion and exclusion criteria based on then-current electronic medical record data are said to have an index visit and included in the study. The only exception to universal eligibility screening is the rare occasion when a network-wide outage or other large-scale event prevents the algorithms from running. Such events are exceedingly rare, and we assume that unscreened yet eligible patients are equally distributed across treatment groups.

5.5 STRATEGIES FOR RECRUITMENT AND RETENTION

Based on endorsement and support for CDS by the medical leadership, the 32 largest clinics meeting the criteria for eligibility were included in the study with leadership approval. The CDS intervention was integrated into the routine care and workflow for patients in the clinics. Several strategies used successfully in previous studies were adopted to ensure high use rates of the CDS at the point of care. These include:

[figure not shown]
1. Training sessions for clinic staff either in-person or through live or taped webinars (with lunch provided) prior to the onset of the intervention to stress the importance of the intervention to patients and describe the recommended workflow.
2. Reliance on nursing staff rather than providers to print the CDS tools when a best practice advisory (BPA) pops up during the rooming process for patients who meet the study edibility criteria.
3. Setting a goal with providers and clinics staff to print the CDS tools at 75% or more of eligible encounters and sending clinic leaders frequent reports of CDS print rates at the clinic and provider levels.
4. Outreach phone calls and emails to clinic leaders if print rates at an intervention clinic drop below goal.
5. Assessing end user experience and collecting feedback throughout the intervention period and being responsive as needed to improve the CKD-CDS tools and intervention overall.

